6.4. Study Intervention Compliance

Treatment compliance information for study treatment will be collected through patient dosing diaries and/or solid oral dosage unit counts at each visit, with the number of dosage units taken relative to the number expected to be taken summarized for each cycle. The patient must take \geq 80% of the planned doses for study treatment in a cycle to be deemed compliant. Dose suspensions or delays may occur and will not result in a patient being considered as noncompliant. A patient may be considered noncompliant if judged by the investigator to have intentionally or repeatedly taken \geq 125% of the planned doses of study treatment in a cycle. Deviation(s) from the prescribed dosage regimen should be recorded in the eCRF.

Study intervention will be administered under medical supervision by the investigator or designee. The dose of study intervention and study participant identification will be confirmed prior to the time of dosing. The date and time of each dose administered will be recorded in the source documents and in the CRF.

6.5. Concomitant Therapy

Any medication or vaccine (including over-the-counter or prescription medicines, vitamins, and/or herbal supplements) that the patient is receiving at the time of enrollment or receives during the study and after the last dose of study treatment at the short-term follow-up Visit (See Schedule of Activities, Section 1.3) must be recorded in the eCRF and should be updated throughout the patient's participation in the study along with

- reason for use, and
- dates of administration, including start and end dates.

The Sponsor CRP/CRS should be contacted if there are any questions regarding concomitant or prior therapy.

Medications not permitted (All Arms)

Anticancer therapies for cancer (including ET, chemotherapy, immunotherapy) will not be permitted while patients are on study treatment. Use of megestrol acetate as an appetite stimulant is not permitted.

Strong inducers of CYP3A4 should also be avoided in patients receiving exemestane on-study.

Imlunestrant Guidance

The information in this section is provided for guidance to investigators and does not preclude the use of these medications if clinically indicated.

CYP Substrates

In vitro assays indicated that imlunestrant is a time-dependent inhibitor of CYP2C8, CYP2C9, CYP2C19, and CYP3A. Imlunestrant is also predicted to be a clinically relevant reversible inhibitor of CYP2B6, CYP2C19, CYP2C8, CYP2C9, and CYP2D6. As a result, caution should be used with concomitant medications that are sensitive substrates of CYP2B6, CYP2C8, CYP2C9, CYP2C9, CYP2C19, CYP2D6, and CYP3A4, or substrates of these CYPs with a narrow therapeutic index. A week of washout time following imlunestrant treatment is advised before

starting sensitive substrates of CYP2C8, CYP2C9, CYP2C19, and CYP3A (Section 10.11 Appendix 11, Section 10.12 Appendix 12, and Section 10.13 Appendix 13).

UGT1A1, P-gp and BCRP

According to preclinical studies, UGT1A1 is involved in the metabolism of imlunestrant. As a precaution, strong inducers and inhibitors of UGT1A1 should be avoided (Section 10.14 Appendix 14).

Due to limitations of in vitro assessments, the impact of imlunestrant as an inhibitor to P-gp and the Breast Cancer Resistance Protein (BCRP) in the gut wall cannot be ruled out. Therefore, caution should be exercised when co-administrating imlunestrant with narrow therapeutic index substrates of P-gp and BCRP (i.e. digoxin).

Consult the IB for additional information.

Abemaciclib Guidance

The information in this section is provided for guidance to investigators and does not preclude the use of these medications if clinically indicated.

Modulators of CYP3A

Abemaciclib is extensively metabolized through oxidation by CYP3A. In clinical drug interaction studies,

- coadministration of clarithromycin, a strong CYP3A inhibitor, increased exposure (AUC) of abemaciclib by 3.4-fold (Study I3Y-MC-JPBE), and
- coadministration of rifampin, a strong CYP3A inducer, decreased exposure of abemaciclib by 95% (Study I3Y-MC-JPBF).

Strong inhibitors of CYP3A (given via non-topical routes of administration) should be substituted or avoided if possible (Appendix 11, Section 10.11). This includes grapefruit or grapefruit juice. In particular, avoid oral administration of the very strong CYP3A inhibitor, ketoconazole.

If coadministration with a strong CYP3A inhibitor is unavoidable, investigators should reduce the dose of abemaciclib by 50 mg at the start of CYP3A inhibitor treatment. That is, for patients receiving 150 mg twice daily, reduce the dose to 100 mg twice daily. For patients who have already had dose reduced to 100 mg twice daily for tolerability, reduce the dose further to 50 mg twice daily. Alternatively, the investigator may consider suspending abemaciclib for the duration of the CYP3A inhibitor medication.

Upon discontinuation of the strong CYP3A inhibitor, the dose of abemaciclib may be reescalated to the dose that was used before starting the strong inhibitor after a sufficient washout period (3 to 5 half-lives of the strong inhibitor). Re-escalation of the abemaciclib dose requires review and approval from the Sponsor CRP/CRS.

Inducers of CYP3A should be substituted or avoided if possible (Appendix 11, Section 10.11). Coadministration with a CYP3A inducer \geq 28 days must be discussed with the Sponsor CRP/CRS.

Transporter Substrates

Abemaciclib inhibits the transporters P-glycoprotein, breast cancer resistance protein, organic cation transporter 2, multidrug and toxin extrusion protein 1 (MATE1), and MATE2-K. The observed serum creatinine increase in clinical studies with abemaciclib is likely due to inhibition of tubular secretion of creatinine via OCT2, MATE1, and MATE2-K. In vivo interactions of abemaciclib with narrow therapeutic index substrates of these transporters, such as digoxin and dabigatran, may occur.

6.5.1. Palliative Medicine and Supportive Care

Patients should receive full supportive care to maximize quality of life. Patients will receive supportive care as judged by their treating physician. If it is unclear whether a therapy should be regarded as supportive care, the investigator should consult the Sponsor CRP. Use of any supportive care therapy should be reported in the eCRFs.

Palliative radiation therapy is permitted after discussion with and agreement of the Sponsor CRP/CRS or designee for irradiating small areas of painful metastases that cannot be managed adequately using systemic or local analgesics. Such areas must not be an identified target lesion and must not constitute progressive disease or meet RECIST v1.1 criteria for progressive disease. Any symptomatic deterioration or clinical disease progression requiring, in the opinion of the investigator, other forms of specific antitumor systemic therapy, will be cause for discontinuation of study therapy.

In addition, any disease progression requiring other forms of specific antitumor therapy will also necessitate discontinuation from the study. Appropriate documentation for all forms of premedications, supportive care, and concomitant medications must be captured on the CRF.

The use of granulocyte-colony stimulating factor is permitted at the discretion of the investigator based on ASCO (Smith et al. 2015) and European Society for Medical Oncology (Crawford et al. 2009) guidelines.

If clinically indicated at any time during the study, erythropoietin and packed red blood cell transfusions may be used according to ASCO guidelines (Rizzo et al. 2008). Prophylactic antibiotic treatment should be consistent with ASCO guidelines (Flowers et al. 2013).

Patients with bone metastases present on baseline imaging should be appropriately treated with bisphosphonates or RANK-L targeted agents (for example, denosumab), per respective approved labels. Initiation of treatment with bone-modifying agents must begin at least 7 days prior to randomization. Patients receiving bisphosphonates or RANK-L targeted agents should not switch treatments (for example, replace a bisphosphonate with denosumab) while on study treatment. However, exceptional cases without evidence of PD may be considered in consultation with the Lilly CRP. These exceptional cases will not incur a protocol deviation.

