7.1. Participant Discontinuation/Withdrawal from Study Treatment

Patients will be discontinued from study treatment in the following circumstances:

- at any time at his or her own request
- at the request of his or her designee (for example, parents or legal guardian)
- at the discretion of the investigator for safety, behavioral, compliance, or administrative reasons
- if the participant becomes pregnant during the study See Section 8.3.2 regarding regulatory reporting requirements
- if enrollment in any other clinical study involving an investigational product or enrollment in any other type of medical research judged not to be scientifically or medically compatible with this study
- if the participant, for any reason, requires treatment with another therapeutic agent that has been demonstrated to be effective for treatment of the study indication, discontinuation from the study occurs prior to introduction of the new agent
- if the participant is significantly noncompliant with study procedures and/or treatment
- disease progression. Exceptions for continuing study treatment beyond confirmed radiographic progression may be made on a case-by-case basis for patients who are believed to be clinically benefiting from study treatment, and the investigator and the Sponsor agree that continuing study treatment is in the patient's best interest, and
- unacceptable toxicity.

Participants who discontinued from the investigational product prematurely for any reason will remain in the study and have short-term and long-term follow-up procedures as outlined in the SoA, Section 1.3.

If the participant withdraws consent for disclosure of future information, the Sponsor may retain and continue to use any data collected before such a withdrawal of consent. If a participant withdraws from the study, he or she may request destruction of any samples taken and not tested, and the investigator must document this in the site study records.

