7.2. Discontinuation from the Study

In rare instances, it may be necessary for a participant to permanently discontinue (definitive discontinuation) study intervention. If study intervention is definitively discontinued, the participant will remain in the study to be evaluated for survival. See the SoA for data to be collected at the time of discontinuation of study intervention and follow-up and for any further evaluations that need to be completed.

Patients will be discontinued from the study in the following circumstances:

- the Sponsor determines that participation in the study needs to be stopped for medical, safety, regulatory, or other reasons consistent with applicable laws, regulations, and GCP
- the investigator decides the patient should be discontinued from the study
- the patient requests to be withdrawn from the study, and
- the study has been completed.

If a clinically significant finding is identified (including, but not limited to changes from baseline in QT interval corrected using Fridericia's formula (QTcF)) after enrollment, the investigator or qualified designee will determine if the participant can continue in the study and if any change in participant management is needed. This review of the electrocardiogram printed at the time of collection must be documented. Any new clinically relevant finding should be reported as an AE.

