8.1.2. Efficacy Assessments during Post-discontinuation Follow-Up

Post-discontinuation follow-up during the study period will be conducted as described in the SoA (Section 1.3). For those patients who are randomized and never receive study treatment or those who discontinue study treatment without objectively measured PD, the investigative sites will continue to monitor patients and periodically evaluate tumor response approximately every 8 weeks for the first 12 months with the first assessment relative to Cycle 1 Day 1 and thereafter approximately every 12 weeks by the same method used at baseline and throughout the study until the patient has objective disease progression, death, start of a new anticancer therapy or study completion. In addition, anticancer therapies initiated after study treatment discontinuation will be collected during this follow-up period.

After the patient has objective disease progression, radiologic imaging and photographic images are no longer required and the patient will be followed up approximately every 12 weeks until the patient's death or overall study completion. Lilly will continue to collect survival data on all patients but may reduce data collection for other efficacy data. Sponsor will notify investigators when this reduced data collection can begin.

Tumor assessments will be performed for each patient at the times shown in the SoA (Section 1.3).

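### Protocol Section 6.5.1 and one Section 7.1 bullet send participants who need other anticancer therapy out of the study, contradicting the sections that keep them in it for survival follow-up

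*Protocol*

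**What the plan says.** Two passages order exit from the study:

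- Section 6.5.1 (supportive care). Clinical deterioration or progression that calls for other systemic therapy "will be cause for discontinuation of study therapy". The next sentence adds that "any disease progression requiring other forms of specific antitumor therapy will also necessitate discontinuation from the study". The section therefore uses two different terms side by side.
- Section 7.1, bullet on needing another effective agent: "discontinuation from the study occurs prior to introduction of the new agent". The list holding this bullet opens with "Patients will be discontinued from study treatment in the following circumstances", so it sits under a treatment-discontinuation heading.

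The other passages say or assume the opposite:

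- Section 7.1, closing text: "Participants who discontinued from the investigational product prematurely for any reason will remain in the study and have short-term and long-term follow-up procedures".
- Section 7.2, after definitive discontinuation of study intervention: "the participant will remain in the study to be evaluated for survival". Its list of reasons for leaving the study names neither progression nor new therapy.
- Section 7.3: vital status is sought for every randomized patient.
- Section 8.1.2, after objective progression: "radiologic imaging and photographic images are no longer required and the patient will be followed up approximately every 12 weeks", until death or study completion, with survival data still collected on all patients.
- Schedule of Activities (Section 1.3): long-term follow-up runs to death or study completion. It collects survival, may collect later anticancer therapies, and asks for the date of progression on the first of them.

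**The concern.** OS carries three error-controlled key secondary hypotheses (H4, H5 and H6 in SAP Section 4.3.3). PFS2, time to chemotherapy and chemotherapy-free survival also need data from after study treatment stops.

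SAP Section 4.4.1.1 censors OS at the last date the participant is known to be alive. A site that acts on Section 6.5.1 or the Section 7.1 bullet would record the participant as off study before next-line therapy, and OS could then be censored at about that point. Such censoring is informative, because the trigger is worsening disease. If PFS differs between arms, the timing of these exits differs too, and the trial is open-label. Because exit comes before the new agent is introduced, the start of chemotherapy could itself go unrecorded, and progression on the next line would be lost.

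**Working it through.** **1. Can both sets of instructions be followed?** No. The Schedule of Activities asks for the date of progression on the first later anticancer therapy. That date cannot be collected under the study schedule from someone who left the study before that therapy began.

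**2. Are the SAP's OS figures sound?** Yes. Table 4.1 was re-derived with the SAP's Lan-DeMets O'Brien-Fleming formula at one-sided alpha 0.00693978, with critical HR = exp(−2z/√d) for d deaths.

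- Final look: d = 390 and p = 0.0059 (z about 2.52) give exp(−2 × 2.52/√390) = 0.775, as stated.
- Look 1: its event count is not printed. From p = 1.4E-05 (z about 4.19) and HR 0.504, d = (2 × 4.19/ln 0.504)² ≈ 150.
- At 150/255/330/390 deaths the critical HRs are 0.504/0.675/0.740/0.775, matching the table. Tables 4.2 and 4.3 reproduce to within 0.001 on HR.

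**3. Does the OS plan rely on follow-up after progression?** Yes.

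- A vs B: look 1 falls at the final PFS analysis, so about 390 − 150 = 240 deaths come later. At that analysis 640 − 480 = 160 participants have no counted PFS event. Even if all 160 died, at least 240 − 160 = 80 of the later deaths must occur in participants who had already progressed.
- ESR1-mutation detected (Table 4.2): 155 − 65 = 90 deaths come after look 1.
- C vs A (Table 4.3): 260 − 65 = 195 deaths come after look 1.

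**4. What if every site applied the two passages literally?** Two inputs are not in the documents and are assumed:

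- q, the share of the 640 who die without prior progression: 5%, 10% or 20%.
- s, the share of the remaining deaths that occur in participants who had gone on to other anticancer therapy: 50% to 100%.

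Retained deaths = 640q + (390 − 640q)(1 − s). For example, q = 5% and s = 100% gives 32 + 358 × 0 = 32; q = 20% and s = 50% gives 128 + 262 × 0.5 = 259.

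| q (deaths without progression) | s = 50% | s = 70% | s = 90% | s = 100% |
|---|---|---|---|---|
| 5% (32) | 211 | 139 | 68 | 32 |
| 10% (64) | 227 | 162 | 97 | 64 |
| 20% (128) | 259 | 207 | 154 | 128 |

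No cell reaches 390. The shortfall runs from 390 − 259 = 131 to 390 − 32 = 358 deaths.

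**The case against.** The strongest reply is that the governing sections already settle the matter. Section 7.2 deals specifically with leaving the study and keeps participants in it for survival. Section 8.1.2 and the Schedule of Activities, from which sites work, run follow-up to death or study completion. The Section 7.1 bullet sits under a treatment-discontinuation lead-in and is corrected by the end of its own section. On this view only one sentence in a supportive-care paragraph is left uncorrected locally, and nothing in the documents shows that any site has acted on it.

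Much of this stands. It shows that the intent is continued follow-up and that the flaw is one of wording. It does not remove the conflict. Section 6.5.1 uses the treatment term and the study term in consecutive sentences, so a site could fairly take them as different actions. Section 7.2 also lists the investigator's decision as a reason for leaving the study, which gives such a site a route. The vital-status search in Section 7.3 would recover some deaths, but it falls under loss to follow-up, operates within legal and ethical limits, and does not supply PFS2 or later-therapy data.

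A reader might infer that OS follow-up ends for almost everyone at progression, taking 480 of 640 (75%) as the share affected. The documents do not support that. The trigger is needing another therapy, not progression itself; Sections 6.1.1 and 7.1 allow some treatment beyond progression; and the 480 PFS events include deaths without progression.

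**Conclusion.** This is an internal contradiction in operative protocol text that should be corrected. The OS plan is not missing, and the OS event counts and boundaries are not wrong.

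The actual loss is unknown. It depends on how many sites apply the two passages literally and on q and s, none of which the documents give. The 32–259 retained deaths are conditional on full literal compliance and on the assumed ranges, so they bound the harm and do not forecast it. A reader might go further and conclude that the planned 390, 155 and 260 deaths cannot be reached. That would need literal compliance at essentially every site, whereas the rest of the protocol directs sites to keep following participants. The direction of any bias in the OS hazard ratio cannot be determined from the documents.

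**What to change.** Reconcile Section 6.5.1 and the Section 7.1 bullet with Sections 7.2 and 8.1.2 and the Schedule of Activities. Both should refer to discontinuation of study treatment and state that the participant remains in the study for survival and post-discontinuation follow-up. Leave study withdrawal to the reasons in Section 7.2. The rules on when study treatment stops are unchanged.

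Send sites a clarification that also asks them to check for participants already recorded as off study solely because another anticancer therapy was needed.

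The cost is two wording edits, one letter and a site check. No procedure is added to the Schedule of Activities, and no SAP figure changes.

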6.5.2. Supportive Management for Diarrhea

Patients should receive instructions on the management of diarrhea. In the event of diarrhea, supportive measures should be initiated as early as possible. These include

• At the first sign of loose stools, the patient should initiate antidiarrheal therapy (for example, loperamide) and notify the investigator or site personnel for further instructions and appropriate follow-up.

- Patients should also be encouraged to drink fluids (that is, 8 to 10 glasses of clear liquids per day).
- Site personnel should assess response within 24 hours.
- Follow dose modification guidance for imlunestrant (Section 6.6.1) and/or abemaciclib (Section 6.6.3), including dose suspension and/or reduction as appropriate.
- For severe cases of diarrhea, or any diarrhea associated with severe nausea or vomiting, consider
 - o IV fluids with electrolyte replacement
 - o measurement of absolute neutrophil counts
 - o monitor patients for fever
- If diarrhea is associated with fever or severe neutropenia, consider broad-spectrum antibiotics.

6.5.3. Photosensitivity

Based on an in vitro study, exposure to imlunestrant may result in photosensitivity. Patients are advised to avoid direct sun exposure and the use of tanning beds during study administrations period and at least 5 days after the last dose. If patients must be exposed to the sun, they should be advised to wear sunscreen, appropriate sun-blocking clothing, and sunglasses.

6.6. Dose Modification

General Considerations for Dose Delays.

In addition to the permitted protocol windows (see Schedule of Activities, Section 1.3), treatment cycles may be delayed up to 7 days due to holidays, weekends, bad weather, or other unforeseen circumstances and will not be deemed a protocol violation.

In exceptional cases, for planned delays (including but not limited to vacation or holidays), additional study drug may be dispensed.

When a study drug is delayed, if possible and appropriate, patients should resume study treatment within 1 treatment cycle and, if not possible, then every effort should be made to start on the first day of the next dosing cycle. In rare circumstances, a delay of >28 days may be permitted before permanent treatment discontinuation, as long as the patient has clinical benefit without objective disease progression and is recovering from the toxicity. Such circumstances must be discussed with the Sponsor CRP/CRS. All dose modifications should be documented, including the approach taken and a clear rationale for the need for modification.

Dose Modifications for Imlunestrant

Management of some adverse reactions may require dose interruption and/or dose reduction. If dose reduction is necessary, decrease the dose by 200 mg. Discontinue imlunestrant for patients unable to tolerate 200 mg QD. In the event that imlunestrant must be discontinued, a participant may continue to receive abemaciclib (Arm C only).

Refer to the tables below for further details on dose modification and management.

Dose Adjustment	Oral Dose Imlunestrant	Frequency
0	400 mg	QD
1	200 mg	QD

Table 1: Imlunestrant Dose Reduction Guidelines

Abbreviation: QD = once daily.

6.6.1. Imlunestrant Dose Adjustments for Treatment-Emergent, Related*, and Clinically Significant Adverse Events

Treatment-emergent laboratory abnormalities of neutrophil count decreased and/or ALT/AST increased, regardless of clinical significance, must follow the dose adjustment table below.

*Related means there is a reasonable causal relationship with imlunestrant.

Toxicity Type	Toxicity Profile and Severity	Dose Suspension	Dose Reduction
Hematologic	Grade 3	Dose MUST be suspended until toxicity resolves to at ≤Grade 2	Not required
toxicity	Grade 4 or Recurrent Grade 3	Dose MUST be suspended until toxicity resolves to at ≤Grade 2	Resume at next lower dose level
If Patient Requires Administration of Blood Cell Growth Factors	Regardless of severity	Dose MUST be suspended until toxicity resolves to at least Grade 2 and a minimum of 48 hours after growth factor administration	Resume at next lower dose unless the dose was already reduced for the toxicity that led to the use of the growth factor (that is, second dose reduction not required)
Febrile neutropenia	Regardless of severity	Dose MUST be suspended until toxicity resolves	Resume at next lower dose level
Nonhematologic toxicity (except diarrhea, alopecia, and	Persistent or recurrent Grade 2 that does not resolve with maximal supportive measures within 7 days to baseline or Grade 1	Dose MUST be suspended until toxicity resolves to baseline or Grade 1	Not required
hepatotoxicity) ^a	Grade 3 or 4 (except non- hepatic asymptomatic laboratory changes)	Dose MUST be suspended until toxicity resolves to baseline or Grade 1	Resume at next lower dose level
	AST/ALT >ULN - 5.0×ULN	Not required	
Hepatotoxicity	Persistent or Recurrent: AST/ALT >3.0-5.0×ULN	Dose MUST be suspended until toxicity resolves to baseline or to >ULN- 3.0×ULN	Not required

Toxicity Type	Toxicity Profile and Severity	Dose Suspension	Dose Reduction	
	AST/ALT >5.0-20×ULN Or ALT or AST \geq 3 × baseline (if ALT or AST \geq 1.5 × ULN at baseline) or AST/ALT >8 × ULN (whichever is the lower threshold)	Dose MUST be suspended until toxicity resolves to baseline or to ALT/AST>ULN - 3.0×ULN	Resume at next lower dose level	
	AST/ALT >20.0×ULN Or			
	ALT or AST \ge 3 × ULN concurrent with TBL \ge 2 × ULN (if ALT or AST < 1.5 × ULN at baseline), in the absence of cholestasis	Discontinue imlunestrant		
	Or ALT or AST $\geq 2 \times$ baseline concurrent with TBL $\geq 2 \times$ ULN (if ALT or AST $\geq 1.5 \times$ ULN at baseline), in the absence of cholestasis			
	Grade 1	Not re	quired	
	Grade 2 that does not resolve with maximal supportive measures within 24 hours to ≤Grade 1	Suspend until toxicity resolves to ≤Grade 1	Not required	
Diarrhea	Grade 2 that persists or recurs after resuming the same dose despite maximal supportive measures. Requires hospitalization or Grade 3 or 4	Suspend until toxicity resolves to ≤Grade 1	Resume at next lower dose level	
Bloody diarrhea	Any grade	Dose MUST be suspended until bloody diarrhea resolves and diarrhea resolves to Grade ≤1	Resume at next lower dose level	

Abbreviations: ALT = alanine aminotransferase; ASCO = American Society of Clinical Oncology; AST = aspartate aminotransferase; TBL = total bilirubin; ULN = upper limit of normal.

^a Events of diarrhea and hepatotoxicity should follow corresponding guidance listed in the table.

Note: Determination of persistent events will be at the discretion of the investigator. Recurrent toxicity refers to the same event occurring within the next 8 weeks (as measured from the stop date of the first event. As a general guidance, based on the risk/benefit balance assessment per the investigator, for a patient who experiences a new episode of Grade 3 hematological toxicity after more than 8 weeks following the last episode of the same Grade 3

hematological toxicity, the investigator may consider resuming the participant on the same drug dose should the participant satisfy the following conditions:

- The participant showed stable hematological counts (Grade <2) during that timeframe
- In the absence of any infectious sign or risk factor
- The participant is benefiting from study intervention.

